Appendix 3: Calculation of Morphine Milligram Equivalents (MME) ([back](#))

Opioid	To convert to oral morphine milligram equivalent (MME), multiply dose of drug (in mg) by:*
Codeine	0.15
Hydromorphone	5
Morphine	1
Oxycodone	1.5
Tramadol	0.15
*Conversion ratios for opioids can vary based on individual patient drug metabolism, which may be influenced by genetics and other medications.	
Fentanyl 0.01 (10mcg) IV = Equivalent to Morphine 5mg	

Table is adapted from National Guidelines for Opioid Conversion^{97,98} and local Health Authority Opioid Conversion Table for Fentanyl.⁹⁹

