Preliminary evidence of efficacy: Although severe acute post-operative pain is not the only risk factor for chronic post-surgical pain (CPSP), an intervention that does not decrease postoperative pain is unlikely to have a significant impact on CPSP. If the 80%

confidence interval for the between-group difference in average pain score in the 24-hour postoperative period favours LA block, we will consider that preliminary evidence of efficacy.^{65,66}

Secondary outcomes of the pilot trial include adverse events related to study interventions. We will also collect the outcomes for the definitive trial to test and refine data collection processes.

The primary outcome in the definitive trial is chronic pain, defined by the Pain Burden Index, measured at 3 and 6 months following surgery. The Pain burden Index examines postsurgical pain in four postoperative body areas. The Index is calculated as a sum of the four locations (breast, chest, axilla, arm) multiplied by the frequency of pain¹² (see Form 8: Pain Burden Index).

Secondary outcomes of the definitive trial include:

- Opioid analgesia requirements during surgery and in the first 24 hours after surgery, defined as morphine milligram equivalents (MME). The total MME will include intraoperative opioids administered in the OR and postoperative opioids administered/ingested in the Postanesthetic Care Unit (PACU), Surgical Day Care Unit (SDC), Inpatient Unit, and home in the 24-hour period after completion of surgery. Opioids consumed will be converted to MME (see Appendix 3: Calculation of Morphine Milligram Equivalents (MME)).
- Acute patient-reported pain scores:
 - Numerical Rating Scale (NRS; 11-point scale) measured at the standard time points of nursing care assessments: preoperatively (baseline); four times per hour in PACU until discharge; if admitted, hourly for 2 hours, and then every 6 hours in the Inpatient Unit; and at discharge from hospital; 24 hours after surgery is complete.
- Opioid-induced side effects:
 - Postoperative nausea and vomiting
 - Nausea severity (by Verbal Rating Scale) in PACU
 - Vomiting episodes (0-48 hours after surgery) in PACU & home
- Quality of recovery (Form 7: Quality of Recovery-15 Questionnaire)

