10. Pecs I block: Infiltrate will be injected into the fascia between the pectoralis minor and pectoralis major muscles at the level of the 3rd rib in the mid-to-lateral 1/3 of the clavicle in a transverse to oblique orientation. Identification of the pectoral branch of the thoracoacromial artery will assist with needle placement. The needle will be inserted from medial/superior to lateral/inferior. Visual confirmation will be by ultrasound upon visualizing the separation of tissue layers with the injected infiltrate.
11. The needle and probe will be removed and the injection site wiped dry.
12. The patient will be continuously monitored in the block area until ready for transport to the operating room for surgery.

Appendix 2: Evidenced-Based Multimodal Perioperative Analgesia and Anti-emetic Management Protocol for Alloplastic Immediate Breast Reconstruction ([back](#))

PREOPERATIVE

- 1- Patient Education:
 - a. Information on options, risks/benefits, recovery ⁷³⁻⁷⁶
- 2- Fasting & Nutrition:
 - a. Allow clear fluids up to 2 hours before arrival to the hospital and no solid foods after midnight ^{26,77-79}
- 3- Preoperative Analgesics: ²¹ to be given in preop 30 minutes to 2 hours pre-induction
 - a. Gabapentin 600mg po x1 ^{27,80-84}
 - b. Acetaminophen 1000mg po x 1
 - c. Celecoxib 400mg po x 1²¹
 - d. Midazolam 1-4mg IV PRN during nerve block administration only
 - e. Fentanyl 25-100mcg IV PRN during nerve block administration only
- 4- Preoperative anti-emetics: to be given in block room
 - a. Dexamethasone 8mg IV ⁸⁵⁻⁹²
 - i. by Anesthesiologist in block room by slow infusion
- 5- Preoperative Antibiotics: to be given in block room
 - a. Preoperative antibiotics within 60 minutes of incision ⁹³
 - i. by Anesthesiologist in block room
- 6- Regional Anesthesia: Paravertebral block with Pecs I (TPVB+)^{57,94} (Intervention)
 - a. Paravertebral T3/4 block: 0.3% ropivacaine+1:400K epi x 25mL
 - b. Pecs I block with 0.3% ropivacaine with 1:400 epi x 10mL
 - c. TOTAL nerve block LA volume 0.3% ropivacaine x 35 mL = 105mg for 50kg patient

INTRAOPERATIVE

- 1- General Anesthesia
 - a. Induction with Propofol (2-4mg/kg IV), Fentanyl (1-4mcg/kg IV), Rocuronium (0.5-1.2mg/kg IV)
 - b. Endotracheal intubation
 - c. Maintenance with inhalational Sevoflurane (0.6-1.2 MAC)
 - d. Opioid as needed for hemodynamic stability (eg. Fentanyl 0.25-1mcg/kg IV boluses, Hydromorphone to maximum 2mg IV or Morphine to maximum 15mg IV)

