 - e. Ondansetron 4mg IV 30 mins before emergence from general anesthesia ^{85,86,88,95}
 - f. Reversal of muscle relaxant at discretion of OR anesthesiologist with Neostigmine or Sugammadex IV
- 2- Sequential Compression Devices & Warming blanket
- 3- Breast block: 18cc of [0.25% bupivacaine with 1:400 000 epinephrine] diluted in 18cc of NS to give total volume of 36cc of [0.125% bupivacaine with 1:400 000 epinephrine] per patient prior to incision

POSTOPERATIVE (POSTANESTHETIC CARE UNIT)

- 1- Celecoxib 200mg po x1 ²¹
- 2- Acetaminophen 1000mg PO q6h ⁹⁶
- 3- Ondansetron 4mg po/IV q6h
- 4- Gravol 25-50mg po/IV q4-6h PRN
- 5- Hydromorphone 0.2-0.4mg IV q5min PRN
- 6- Fentanyl 25mcg – 50mcg IV q15min PRN
- 7- Oxycodone 5mg-10mg po q4h PRN

POSTOPERATIVE (INPATIENT UNIT)

- 1- Celecoxib 200mg po bid for 2 doses ²¹
- 2- Acetaminophen 1000mg PO q6h ⁹⁶
- 3- Ondansetron 4mg po/IV q6h for 72 hours
- 4- Gravol 25-50mg po/IV q4-6h PRN
- 5- Hydromorphone 0.2-0.4mg IV q5min PRN
- 6- Oxycodone 5mg-10mg po q4h PRN
- 7- Gabapentin 200mg po qhs ^{20,21}
- 8- Keflex 500mg po qid for 7 days

PRESCRIPTION (At discharge, as per instructions in Recovery Booklet)

- 1- Tramacet 1 – 2 tablets po q6h (40 tablets) ²¹
 - i. After Tramacet finished, Acetaminophen 500mg po qid
- 2- Celecoxib 200mg po bid for 2 doses ²⁰
 - i. After celecoxib finished: Ibuprofen 400mg po tid ^{20,21}
 - ii. Note: if discharge delayed, order for celecoxib adjusted for a maximum of 2 doses after discharge from PACU
- 3- Gabapentin 200mg po qhs for 2 doses ^{20,21}
 - i. Note: if discharge delayed, order for gabapentin adjusted for a maximum of 2 doses after discharge from PACU
- 4- Ondansetron 4mg po qid for 72 hours
 - i. Note: if discharge delayed, order for ondansetron adjusted for a maximum duration of 72 hours after discharge from PACU
- 5- Keflex 500mg po qid for 7 days
 - i. Note: if discharge delayed, order adjusted to complete a 7-day course

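### Appendix 3 gives no administration route for its five opioid factors, so IV morphine scores as oral morphine in the MME total and the basis of the hydromorphone factor is unknown

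*Protocol*

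**What the plan says.** Under Outcome Measures, opioid requirement during surgery and over the next 24 hours is a secondary outcome of the definitive trial, and the pilot collects it. The protocol states: "The total MME will include intraoperative opioids administered in the OR and postoperative opioids administered/ingested in the Postanesthetic Care Unit (PACU", and continues through surgical day care, the inpatient unit and home. It adds "Opioids consumed will be converted to MME" and refers the reader to Appendix 3.

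The Appendix 3 column is headed "To convert to oral morphine milligram equivalent (MME), multiply dose of drug (in mg) by". The factors are codeine 0.15, hydromorphone 5, morphine 1, oxycodone 1.5 and tramadol 0.15. No route is given for any of the five, and the only caveat concerns individual metabolism. A separate line reads "Fentanyl 0.01 (10mcg) IV = Equivalent to Morphine 5mg". The source note attributes this line to a "local Health Authority Opioid Conversion Table for Fentanyl", while the other factors come from national guidelines.

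Appendix 2 lists the drugs to be converted. For the operating room it gives, within a list of examples, "Hydromorphone to maximum 2mg IV or Morphine to maximum 15mg IV". For PACU and again for the inpatient unit it gives "Hydromorphone 0.2-0.4mg IV q5min PRN". Oxycodone (PACU and inpatient unit) and Tramacet (at discharge) are oral. No oral morphine or oral hydromorphone is listed.

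**The concern.** The total is expressed on an oral scale, but two of the drugs that feed it are listed only by the IV route. The appendix treats route as relevant for fentanyl and is silent on it for the other two IV opioids. If the factors apply to swallowed doses, IV milligrams enter the sum at the wrong weight next to oral oxycodone and tramadol. The total then depends on drug and route as well as on opioid need.

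The stake is the definitive trial's opioid result. Outcome Measures ranks it as secondary, but the Objectives name opioid consumption among both the primary and the secondary aims of that trial. The pilot collects the outcome in order to test and refine data collection, so this is the stage at which to settle the rule.

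**Working it through.** The protocol prints no worked MME total, so there is no stated figure to reproduce. The check applies the printed rule to the listed doses.

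**Rule.** MME = dose in mg × Appendix 3 factor.

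**Assumption.** Let k be the number of oral milligrams that one IV milligram counts for. The documents give no value. I use k = 1 to 3 as an illustration; k = 1 means that route makes no difference.

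**Morphine** (factor 1; Appendix 2, operating room, ceiling 15 mg IV)
- As printed: 15 × 1 = 15 MME, the same as 15 mg by mouth.
- With k: 15 × k = 15 to 45 MME.
- For comparison, oral oxycodone 10 mg scores 10 × 1.5 = 15 MME. The printed rule scores the two doses equally; for any k above 1 it would not.

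No further assumption is needed to see that route is ignored here: morphine converted to oral morphine with a factor of 1 is an IV-to-oral ratio of exactly 1.

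**Hydromorphone** (factor 5; Appendix 2, operating room ceiling 2 mg IV, single PACU or ward dose 0.2 to 0.4 mg IV)
- As printed: 2 × 5 = 10 MME; 0.2 × 5 = 1 and 0.4 × 5 = 2 MME.
- If 5 is the factor for an oral dose: 10k = 10 to 30 MME for 2 mg. For a single PACU or ward dose, 1k = 1 to 3 and 2k = 2 to 6 MME.
- If 5 is the factor for an IV dose: 10, 1 and 2 MME are already on the oral scale, and none of the listed doses is misconverted.

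The column heading fixes the target unit. It does not say by which route the hydromorphone was given, so the document cannot decide between these two cases.

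**Fentanyl** (10 mcg IV = morphine 5 mg)
- Factor: 5 / 0.01 = 500 per mg.
- If the reference morphine is oral, 10 mcg scores 5 MME as printed. If it is IV, 10 mcg would score 5k = 5 to 15 MME on the oral scale. The line does not say which.

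**Effect on a comparison.** A between-group difference of d mg of IV morphine contributes d to the difference in total MME as printed, and kd = d to 3d on the assumed range. Differences in oral oxycodone or tramadol are not rescaled.

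**The case against.** The strongest reply is that little depends on this. MME is not among the pilot's progression criteria, which concern enrolment, block success, retention and the 80% confidence interval for pain. The sample size does not use it. Both groups share the same table, and the operating-room, PACU and ward staff are blinded. Morphine appears once, as a ceiling dose in a list of examples and as an alternative to hydromorphone, so actual exposure may be small. Raw medication data come from charts and the electronic record, so MME could be recomputed later. Forms 6 and 11 are not shown and may already capture route. All of this stands, and it limits the severity. It does not remove the mismatch, because Outcome Measures prescribes Appendix 3 and Appendix 3 prints the rule. This is something the protocol fixes, not something it leaves to an analysis plan.

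A reader might infer more than the documents support:
- **That IV hydromorphone is shown to score as if swallowed, or to rank wrongly against oral oxycodone.** Both require the factor 5 to be an oral-dose factor, which is not stated.
- **That the fentanyl factor is wrong because it weighs heavily in the sum.** A large weight is not an error. Under the column heading, oral reference morphine is the natural reading, and the cited source is not available here.
- **That the whole appendix ignores route.** The fentanyl line is marked IV.
- **That the comparison is biased towards one group.** With a shared table and blinded staff, the documents support added noise and a difference whose size is hard to interpret. If the block mainly reduces IV use and k exceeds 1, the printed morphine factor would understate that part of the difference, but this is conditional.

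**Conclusion.** The point holds as a defect in the definition of an outcome; no calculation in the protocol fails to reproduce. For morphine it follows from the text alone that the printed rule equates IV and oral milligrams. Its size at the listed ceiling is 15 MME against 15 to 45, and nothing changes at a ratio of 1. For hydromorphone, what is established is that the route behind the factor is unstated; the 10 against 10 to 30 MME applies only if 5 is an oral factor. For fentanyl, what is established is that the reference route is unstated. All the ranges rest on the assumed ratio of 1 to 3.

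The consequence is confined to the size and interpretability of the opioid total. Severity is minor to should-fix: the pilot's decisions do not depend on it, but the rule would carry into the definitive trial.

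**What to change.** Before any dose is converted, replace Appendix 3 with a drug-by-route table on one stated reference route, oral morphine:
- Give morphine and hydromorphone separate IV and oral rows, with factors taken from the sources the appendix already cites.
- State the route to which the codeine, oxycodone and tramadol factors apply.
- State whether the morphine in the fentanyl line is oral or IV, and check that line against its source.
- Keep drug, amount and route for every opioid dose, so that MME can be recomputed if a factor is revised. Route has to be recorded dose by dose, because the intraoperative list in Appendix 2 is only a set of examples.

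The cost is one table and a route entry per dose, from charts and electronic records that the protocol already uses for opioid data. The change concerns scoring only; no dose is judged or proposed.

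### Appendix 3 does not put IV fentanyl, hydromorphone and morphine on one oral-morphine scale, so induction fentanyl and choice of drug can dominate the 24-hour MME total

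*Protocol*

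**What the plan says.** The multiplier column of Appendix 3 is headed "To convert to oral morphine milligram equivalent (MME), multiply dose of drug (in mg) by". Hydromorphone gets 5, morphine 1, oxycodone 1.5, and codeine and tramadol 0.15 each. No row is split by route. Fentanyl stands below these rows in another form: "Fentanyl 0.01 (10mcg) IV = Equivalent to Morphine 5mg". The fentanyl is IV; the route of the morphine is not stated. The table is attributed to national guidelines and, for fentanyl, to a local health authority table.

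Appendix 2 shows which opioids the conversion will meet:

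- Induction includes IV fentanyl at 1-4 mcg/kg (Intraoperative, item 1a).
- Further intraoperative opioid is given as needed: fentanyl boluses of 0.25-1 mcg/kg, or "Hydromorphone to maximum 2mg IV or Morphine to maximum 15mg IV" (item 1d).
- The PACU list has "Hydromorphone 0.2-0.4mg IV q5min PRN" directly above "Fentanyl 25mcg – 50mcg IV q15min PRN", with oral oxycodone 5-10 mg every 4 hours as needed below them.

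Under Outcome Measures, opioid requirement during surgery and the first 24 hours is a secondary outcome of the definitive trial, and "The total MME will include intraoperative opioids administered in the OR" as well as postoperative opioid. The Objectives section also names opioid consumption among the primary objectives of the definitive trial.

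**The concern.** An MME total means something only if every drug and route is scored on the same scale. Here the most heavily weighted drug is IV fentanyl, which patients receive at induction by body weight before there is any postoperative pain. The IV drugs used alongside it are scored with single factors from a table built on oral morphine. Two patients with the same need could then get very different totals because one was given fentanyl in PACU and the other hydromorphone, or because their induction doses differed.

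What is at stake is the sensitivity of the opioid outcome. A real opioid-sparing effect could be lost in this variation. In about 30 patients, a chance imbalance in fentanyl use could also look like an effect. The pilot collects the definitive trial's outcomes in order to test and refine data collection, so an unreconciled table would be carried forward.

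**Working it through.** **Inputs.** Factors come from Appendix 3, doses from Appendix 2, and the 50 kg minimum weight from the Exclusion Criteria. The conversion is a stated constant, so the protocol offers nothing from which to reproduce it. The check is whether doses and factors fit together.

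**1. Fentanyl factor.** 5 mg / 10 mcg = 0.5 MME per mcg (500 per mg).

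**2. PACU, one dose of each, as printed.**
- Fentanyl: 25 × 0.5 = 12.5; 50 × 0.5 = 25 MME.
- Hydromorphone: 0.2 × 5 = 1; 0.4 × 5 = 2 MME.
- Ratio: 12.5/1 = 25/2 = 12.5.

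**3. Allowing for the intervals.** In 15 minutes at maximum frequency, hydromorphone can be given three times (0.6-1.2 mg) and fentanyl once. Hydromorphone then scores 3-6 MME, and the ratio is 12.5/3 = 25/6 = 4.2.

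**4. Allowing for route.** The documents give no IV-to-oral factor, so 2-3 is an assumption.
- Per dose, hydromorphone becomes 2-4 MME (factor 2) or 3-6 MME (factor 3). The ratio is 6.25 or 4.2.
- With the interval allowance as well, it becomes 6-12 or 9-18 MME. The ratio is 12.5/6 = 2.1 or 12.5/9 = 1.4.

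Step 4 treats the 5 mg of morphine in the fentanyl line as oral. If it is parenteral, the same allowance applies to fentanyl too and the ratio returns to 12.5 per dose. The missing route therefore matters.

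**5. Intraoperative, as printed.**
- Hydromorphone maximum: 2 × 5 = 10 MME. Morphine maximum: 15 × 1 = 15 MME.
- Induction fentanyl at 50 kg: 50 × 1 × 0.5 = 25 to 50 × 4 × 0.5 = 100 MME. The lowest induction dose in the lightest eligible patient exceeds either maximum.
- With the assumed factor of 2-3, the maxima become 20-30 (hydromorphone) and 30-45 (morphine). The low end of induction no longer exceeds them all; the high end still does.

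**6. A check on fentanyl amounts the protocol itself cites.** The Pecs Block section quotes trial means for intraoperative fentanyl of 141 (±32) and 218 (±24) mcg. At 0.5 per mcg these score 70.5 and 109 MME. Oxycodone 10 mg every 4 hours for a full day scores 6 × 10 × 1.5 = 90. Taken as SDs, 24-32 mcg correspond to 12-16 MME, about one 10 mg oxycodone dose (15).

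**7. How far induction could dominate.** The protocol gives no expected opioid use, so postoperative use is assumed. Share = induction / (induction + postoperative), from 1 mcg/kg at 50 kg (25 MME) to 4 mcg/kg at an assumed 70 kg (140 MME), with other intraoperative opioid left out:

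| Assumed postoperative use | MME | Induction share |
|---|---|---|
| Light: hydromorphone 0.4 mg × 2, oxycodone 5 mg × 2 | 4 + 15 = 19 | 57-88% |
| Moderate: hydromorphone 0.4 mg × 4, oxycodone 5 mg × 4 | 8 + 30 = 38 | 40-79% |
| Heavy: hydromorphone 0.4 mg × 5, oxycodone 10 mg × 6 | 10 + 90 = 100 | 20-58% |

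A simulation assumed a mean weight of 68 kg (SD 11), an average of three PACU doses, none to half of patients on PACU fentanyl, and 0-6 oxycodone doses of 5 or 10 mg. Induction plus PACU opioid made up 54-91% of the variance of the total if induction doses spread evenly over 1-4 mcg/kg. With narrower dosing (1-2 or 1.5-2.5 mcg/kg) it was 16-86%.

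**The case against.** The strongest reply is that the 12.5-fold figure does not show the fentanyl line to be wrong. The two PACU orders have different intervals, and the protocol nowhere calls them equianalgesic. The table is oral while the hydromorphone is IV. Steps 3 and 4 show that both allowances together leave a ratio of only 1.4-2.1. This stands: part of the gap may come from unrouted factors applied to IV hydromorphone and morphine. It does not remove the point, because Appendix 3 applies neither allowance and anyone following it as printed gets the 12.5-fold scoring.

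A reader might infer a slipped decimal in the fentanyl line. The documents do not support that. The amount appears in two agreeing forms (0.01 and 10 mcg), and the local source table is not available here. A value ten times smaller would score PACU fentanyl at 1.25-2.5 MME against 6-18 for hydromorphone with both allowances, about 5-7 times lower.

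It is also fair that opioid is a secondary outcome, that doses are recorded and totals can be recomputed, and that item 1d opioid is given as needed and so carries real information on requirement. These limit the severity. Recomputing later is a weaker safeguard, since a factor chosen after results are seen by arm would be post hoc.

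**Conclusion.** Wrong as written, and it should be fixed. As printed, Appendix 3 scores IV fentanyl, hydromorphone and morphine on scales that do not match the doses in Appendix 2: 12.5-fold per PACU dose, and 25-100 MME for induction at 50 kg against intraoperative maxima of 10 and 15. These figures are arithmetic on the protocol alone. The smaller PACU gaps (4.2 to 6.25 with an IV-to-oral factor of 2-3; 1.4-2.1 with the interval as well) rest on that assumed factor. Which row or rows cause the mismatch cannot be settled from the documents.

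The 24-hour total can be dominated by induction fentanyl and drug choice. A reader might infer that it mostly reflects them. That does not follow: the protocol gives no usage data, and under heavy oral use or narrow induction dosing the share falls well below half. Nor is this a clear bias between arms. OR anesthesiologists and the OR, PACU and ward nurses are blinded, so the effect is mainly noise and lost sensitivity, plus chance imbalance in a small sample.

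The feasibility criteria and the 80% CI on pain do not use MME. Neither sample size does: the pilot's rests on a pain difference of 1 with SD 1.2, the definitive trial's on chronic pain falling from 50% to 30%.

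**What to change.** Before any data are examined by arm:

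1. Check the fentanyl line and the factors for IV hydromorphone and IV morphine against the conversion sources cited in Appendix 3.
2. Restate Appendix 3 as one factor per drug and route, each with its unit (per mg or per mcg), all on the same oral-morphine basis. State the route of the morphine behind the fentanyl figure.
3. Report intraoperative MME, with induction fentanyl identifiable, separately from postoperative 0-24 hour MME, beside the total already defined.

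The cost is a corrected table and one or two extra derived variables. The Clinical Form already records intraoperative analgesics and postoperative medications, and the Recovery Booklet records use at home. No dosing, visit or sample size changes.

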Appendix 4: PACU and SDC Discharge criteria [\(back\)](#)

PACU Discharge Criteria (1 of 2)

Assessment	Criteria
Neurological Function	
 • Orientated to person, place and time or orientation equivalent to patient's preoperative status. • Obeys commands. • Easy to rouse with a sedation score equal to or less than 2. • Adequate skeletal muscle tone as evidenced by: head lift sustained for minimum 5 seconds and moderate to strong handgrips (or preoperative equivalent). • Full movement and sensation to extremities following general anesthesia or preoperative equivalent.
Respiratory Function	
 • Intact protective airway reflexes: gag, swallow, cough, ability to clear secretions and no artificial airway in place. • Maintains patent airway independently for minimum 30 minutes post-extubation in PACU. • Spontaneous, regular, respirations at a rate 10 to 24/minute. • Maintains SpO₂ at 92% or greater on room air for a minimum of 15 minutes. • Oxygen order from anesthesia is required if patient is unable to maintain oxygen saturation at or above 92% on room air. • No O₂ adjustments for at least 15 minutes prior to discharge. 
Exception: any patient with known or exhibiting signs of OSA will require assessment by anesthesia prior to discharge.

Cardiovascular Function	
 • Blood pressure and heart rate are stable for 3 consecutive 15 minute assessments and within ± 20% of preoperative values. • Cardiac rhythm stable and equivalent to preoperative rhythm (if known). • Extremities warm with evidence of adequate tissue perfusion (or preoperative equivalent).
Thermoregulation	
 • Independently maintains temperature at minimum 36°C. • Temperatures exceeding 38.5°C require consultation with anesthesia prior to discharge.
Gastrointestinal	
 • Post operative nausea is absent or at a tolerable level to the patient following use of rescue anti-emetics/treatment. • If nasogastric tube present, tube is secure, patent and returns are appropriate, i.e. color, consistency and amount within expectation of surgery.

Table is adapted from Providence Health Care Nursing Standards, B-00-1310071- PACU Post Anesthesia Protocol, Published by Providence Health Care, January 2017.

